In a previous pilot study, [name] et al. (2013) assessed the acceptability and feasibility of an evidence-based intervention [i.e., "Easing and Alleviating Symptoms during Treatment" (EASE)] with 24 HNC patients (34% attrition) to improve symptom management, distress, coping, and QoL among HNC patients.⁵⁷ The intervention delivered evidence-based CBT and stress management across eight telephone counseling sessions.⁵⁸ The CBT intervention was found acceptable, feasible, and clinically relevant to HNC patients. [name] et al (2011) administered the same EASE intervention to caregivers of hospice patients in the Caregiver Life Line project (N = 19). In this pilot study.⁵⁹ The CBT intervention included up to 12 weekly telephone calls aimed at fostering adaptive coping skills in the

caregivers. Caregivers were assessed at baseline, 3 months and 6 months for depression, emotional QoL, perceived stress, social support and benefit finding. Results demonstrated a trend toward reduced symptoms of depression and increased emotional QoL (greater reduction at 6 months than at 3 months, suggesting that the benefits of participating in the intervention may become more apparent over time). Caregivers reported high levels of self-efficacy regarding their ability to implement the coping skills learned. These findings demonstrate that the EASE's CBT stress-management intervention is acceptable, feasible and beneficial to caregivers. Based on this evidence, the next step is to conduct a rigorous RCTs to assess whether evidence-based CBT stress-management interventions are equally effective at improving mental health outcomes among underserved LC and HNC patients and caregivers.

IV. Research Methods

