Of the 1,211 patients and 1,211 caregivers (2,422 participants) about 30% will refuse to participate, leaving 848 patients and 848 caregivers (n=1,696) to be screened for randomization. Of these, about 816 patients (47%-57%) will meet exclusion criteria) or refuse further participation (drop-out), based on average participation rates reported in other similar studies. 92 Thus, we estimate that about 444 participants (222 patients; 222 caregivers) will be randomized to one of 2-arms (or 222 per arm). About 44 participants in each arm might drop out of the study, have a member of the couple die, or be lost to follow-up (20% attrition), with 178 participants per arm to remain in the study for the analyses. Figure 1 shows a total of about 356 participants will be available for final analyses. This sample allows us to detect a 0.38 effect size with 90% power.

RCT Conditions/Arms

- Arm 1: Enhanced Usual Care: DHHA, St. Mary's, University of Colorado Hospital, and NJH hospitals provide supportive mental health care for patients such as printed materials, support groups, crisis counseling, and specialized care (e.g., psychiatric medication). Because the amount of usual mental health care that each patient receives varies at each site, we will standardize and monitor the usual care arm across the four sites with an enhanced usual care condition. All participants will receive upon enrollment a "Mental Health Resource Guide" with, (a) web links with mental health resources available at the national and local level, and (b) a list of support groups and mental health care providers to access if they encounter challenges. Participants in the baseline group and enhanced usual care, per usual care practices, with high levels of distress, suicidal ideation and needing specialized care (e.g., psychiatric medication, crisis counseling), will be referred to specialized mental health care following the established protocol at the hospital rather than provided access to the intervention.

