Sample size and power analysis: We estimated minimum effect sizes detectable for different power specifications for various sample sizes. Our target sample size for analyses is 290 patients and 290 caregivers (145 per arm) but we will recruit an initial sample of 222 patients and 222 caregivers (222 per arm) to allow for variability due to 24-34% attrition, based on attrition rates in meta-analyses ⁸⁸ and in our studies. ^{57, 59} If we had a smaller number of participants or if attrition was higher, we would need a minimum of 110 dyads per arm to still be able to detect small to moderate effect sizes. Power is assumed to detect a time by treatment interaction within the proposed repeated measures design. Correlation of measures across time points (rho) was specified as moderate (.4), although sensitivity analyses examined the minimum detectable effect size at alternative specifications of rho and still allow small to moderate effects. Power calculations are for 3 outcomes through a Bonferroni reduction of the significance level to alpha = 0.05/3 = 0.0167. The study is designed to minimize contamination between intervention and control groups (e.g., randomizing both patients and their caregivers to the same group, referrals based on usual care practices). Nevertheless, based on Torgerson, we conservatively powered the study to detect a smaller effect than anticipated in the event of potential contamination.

Analysis approach: Using an intent-to-treat (ITT) approach, primary and secondary outcomes will be analyzed with *linear mixed models* comparing the two groups (*stepped care intervention, usual care*) in patients and caregivers separately.

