Analytic Strategy: Primary and secondary outcomes will be analyzed with linear mixed models comparing the two groups (stepped care intervention, enhanced usual care) in patients and caregivers separately. An alpha level of 0.05 (alpha = 0.05/3 for primary outcomes) will be used to evaluate the a priori planned comparisons. Two-tailed tests will help to detect differences between groups. The study is powered for testing the hypothesis of no group differences in change over the four time points. The software SAS PROC MIXED will be used. 94 For hypotheses addressing group differences for patients and separately for caregivers, outcomes will be evaluated with the same design: 2 groups (stepped care intervention, enhanced usual care) over 4 times (prior to randomization, 6 weeks, 3 months, 6 months). Mixed models will specify group and time and their interaction as fixed effects and subject as a random effect, where subject is assumed independently normally distributed with mean 0 and variance independent of the random errors. A significant group by time interaction is hypothesized, where those in the stepped care intervention are expected to improve to a greater degree than those in the enhanced usual care group. Planned comparisons of group differences at each time point will be conducted in the event of a significant interaction effect. In analyses of caregivers, the model of distress will include the caregiver's age and gender as covariates, as they have been found to be related to their distress; we will also investigate inclusion of patient distress, physical and QoL as covariates. The patient model of distress will include no a priori covariates, but we will explore inclusion of caregiver distress.

Heterogeneous Treatment Effects: To assess how the heterogeneity of the sample may impact treatment effects, a descriptive analysis will be conducted to estimate treatment effects with *standard errors* for important subgroups determined by levels of sex, ethnicity, tumor site (LC vs. HNC), stage (I-II vs. III-IV), hospital site and primary language (English vs. Spanish). Analyses will be based on mixed models for each subgroup. A second analysis will add each factor separately to mixed models for the entire sample. We plan to report on the pre-specified analyses and any post-hoc analyses of subgroups and outcomes analyzed to contribute to the trial's utility and interpretability for implementation and dissemination.

H. Summary of Knowledge to be Gained

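### The stated 90% power at an effect size of 0.38 cannot be reproduced for the declared group-by-time test without an unstated effect pattern or SD unit, and it is not reached at the numbers in the separate patient and caregiver models

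*Combined protocol and SAP*

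**What the plan says.** In section IV.G, the sample size and power paragraph names the test: "Power is assumed to detect a time by treatment interaction within the proposed repeated measures design". It sets the correlation between time points at 0.4 and the significance level by "Power calculations are for 3 outcomes through a Bonferroni reduction of the significance level to alpha = 0.05/3 = 0.0167". The Analytic Strategy paragraph repeats the target, "The study is powered for testing the hypothesis of no group differences in change over the four time points", and specifies two-tailed tests. The mixed model there has group, time and their interaction as fixed effects and a random subject effect, and is fitted to patients and caregivers separately.

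The only numerical power statement is in section IV.C, under Randomization and sample size: "This sample allows us to detect a 0.38 effect size with 90% power". It belongs to a sample of 356, "with 178 participants per arm to remain in the study for the analyses". That sample comes from 444 randomised participants, half patients and half caregivers.

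IV.G also gives an analysis target of 145 per arm, with no power or effect size attached. Of a smaller sample it says "we would need a minimum of 110 dyads per arm to still be able to detect small to moderate effect sizes", without a number for the effect or the power.

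**The concern.** With four visits, the group-by-time interaction is a 3-df test. Its power depends on how the group difference develops over the visits and on the SD in which 0.38 is expressed. The plan gives neither, so the 90% cannot be tied to the declared test. In addition, the 178 per arm adds patients to caregivers, although no primary model contains both.

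The figure will be relied on. A non-significant interaction would be read against a 90% claim, and the planned comparisons at each visit go ahead only after a significant interaction. If the real power is well below 90%, a null result would be given more weight as evidence of no benefit than it deserves.

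**Working it through.** **Inputs from the plan.** Effect size 0.38, 90% power and 178 per arm (IV.C); alpha 0.05/3 = 0.0167, two-sided, correlation 0.4, four visits, random subject effect (IV.G).

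**Assumptions, because the plan is silent.** Time is categorical; there is no group difference at baseline; the largest group difference is 0.38 single-visit SD; correlation is constant; data are complete.

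**The plan's own figure.** The simplest calculation near it is a two-sample t-test at one visit, which uses neither time nor the correlation. With 178 per arm, d = 0.38 and alpha 0.0167 it gives 88.0%; about 188 per arm would be needed for 90%. This is close but not unique. A baseline-to-one-follow-up change contrast with correlation 0.4 and uncorrected alpha 0.05 gives 90.4% at 178 per arm. The source of the 90% cannot be settled from the documents.

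**The declared test.** For the 3-df interaction, with n per arm, group difference δ_t at visit t and mean difference δ̄ over the four visits:

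λ = n × Σ(δ_t − δ̄)² / [2(1 − 0.4)]

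Power is the upper tail of a noncentral F with 3 and 3(2n − 2) df beyond the 0.0167 critical value.

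Worked case, linear growth at n = 178. The differences are 0.38 × (0, 1/3, 2/3, 1). The sum of squares is 0.5556 × 0.38² = 0.0802, so λ = 178 × 0.0802 / 1.2 = 11.9 and power is 70.8%. A simulation of this case gave 71.4%, and one of the constant case at 178 gave 85.7%.

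**Number per model.** 222 patients over two arms is 111 per arm, and 111 × 0.80 = 88.8, so about 89 per arm after IV.C's 20% attrition. The same holds for caregivers.

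**SD-of-change units.** At correlation 0.4 the SD of a change score is √(2 × 0.6) = √1.2 = 1.095 single-visit SDs. Reading 0.38 in those units multiplies λ by 1.2.

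| Pattern at baseline, 6 weeks, 3 and 6 months (× 0.38) | λ at 178 | 178/arm | 89/arm | 178/arm, SD of change | 89/arm, SD of change |
|---|---|---|---|---|---|
| 0, 1/3, 2/3, 1 (linear) | 11.9 | 71% | 34% | 81% | 42% |
| 0, 1/2, 1, 1 | 14.7 | 82% | 44% | 90% | 54% |
| 0, 1, 1, 1 (constant) | 16.1 | 86% | 48% | 93% | 58% |
| 0, 0, 0, 1 (6 months only) | 16.1 | 86% | 48% | 93% | 58% |
| 0, 0, 1, 1 (3 and 6 months only) | 21.4 | 95% | 65% | 98% | 75% |

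The last row is the most favourable possible pattern when the baseline difference is zero and the others lie between 0 and 0.38. The sum of squares is then largest when two of the four differences are at the maximum and two are at zero.

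**Effect detectable with 90% power, single-visit SD units.**

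| Per arm in one model | Constant or 6 months only | Linear | 3 and 6 months only |
|---|---|---|---|
| 89 | 0.57 | 0.66 | 0.49 |
| 110 | 0.51 | 0.59 | 0.44 |

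**The case against.** The strongest reply is that the declared test can reach 90% at 178 per arm. An effect absent at 6 weeks and full at 3 and 6 months gives 95%. A 1-df contrast of the follow-up mean against baseline gives about 94.5% for a constant effect. In SD-of-change units the constant and 6-month-only patterns give 93%. All this stands, so a reader who infers that 90% is impossible at the plan's sample sizes goes too far: the 3-and-6-month pattern also gives 89% at 145 per arm. But the plan states none of these choices. Its only hint about time course is a caregiver pilot with "greater reduction at 6 months than at 3 months, suggesting that the benefits of participating in the intervention may become more apparent over time". That leans towards growth, though it was a trend among 19 caregivers and fixes nothing for patients.

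A reader might also infer that 145 and 110 per arm came from a test without the Bonferroni correction. At d = 0.38 and alpha 0.05, a single-visit t-test gives 89.7% and 80.1%. The documents do not support this inference. IV.G attaches no effect size or power to either number, says that several power specifications were examined, and states the corrected alpha explicitly. The corrected single-visit test at 145 per arm gives 79.5%, an equally conventional design. Likewise, the near match at 178 does not prove that time was ignored: in SD-of-change units, a 1-df change contrast has the same formula as a single-visit test.

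None of these replies helps at 89 per arm, where even the most favourable pattern stays below 90% in either unit.

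**Conclusion.** The concern holds as a power statement that cannot be verified and is not met in the models that will be fitted. At 178 per arm, in single-visit SD units, the declared 3-df test has 71% to 86% power under linear, gradual, constant or 6-month-only effects, and exceeds 90% only under a pattern or unit the plan does not give. At about 89 per arm, the number each separate model can expect, power is 34% to 65%, or 42% to 75% in SD-of-change units.

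These figures assume complete data on those analysed, constant correlation of 0.4, equal variances and categorical time. The 89 uses IV.C's 20% attrition; IV.G's 24% to 34% would leave about 84 to 73 per arm (111 × 0.76 and 111 × 0.66), so power would be lower. How the 90% was originally obtained remains unknown, and the conclusion does not depend on it.

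**What to change.** In the IV.C sample size paragraph and the IV.G power paragraph, replace the 90% claim with the effect detectable by the group-by-time test at two-sided alpha 0.0167 and correlation 0.4. Use the number per arm in each separate model, and state the assumed time pattern and the SD unit. Suggested wording:

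*With about 89 patients per arm (and, separately, 89 caregivers per arm) after 20% attrition, the 3-df group-by-time test at two-sided alpha 0.0167 and correlation 0.4 has 90% power for a maximum group difference of about 0.57 single-visit SD if the effect is constant over follow-up, 0.66 SD if it grows linearly to 6 months, or 0.49 SD if it is present only at 3 and 6 months.*

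Restate the minimum of 110 dyads per arm on the same basis: about 0.51 SD (constant), 0.59 SD (linear) or 0.44 SD (3 and 6 months only). If SD-of-change units were meant, say so and divide these values by 1.095. Correcting the head count alone is not enough, because the pattern and unit would still be undefined.

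The cost is one recalculation, some wording and a less favourable stated figure. Enrolment and the analysis model stay as they are.

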Data aggregation, distributional assumptions, missing data, and attrition: Maximum likelihood techniques will include participants with incomplete data without need for imputation. This technique is robust under certain conditions such that group comparisons will not be biased as long as missing data is ignorable. ^{90, 91} In addition, we will conduct sensitivity analyses to examine the effect of departures from key assumptions (e.g., similarity between groups) made in the main analysis and to help determine effects of missing data. ^{92, 93} This approach will allow us to determine whether the significance of the main analysis was maintained in all sensitivity analyses or was changed in a limited or large number of sensitivity analyses. If this is the case, then separate analyses of only those participants who complete the study will be conducted. To prevent missing data, participants will be administered the measures by research assistants trained on their proper administration. Such an approach is more appropriate for low-literacy populations and maximizes the completion of the measures. During the course of the trial, monthly reports will be generated summarizing recruitment/accrual and completeness of follow-up to allow collaborating sites to proactively follow-up with participants in a timely manner.

Verification of Randomization, Inclusion of Covariates, and Stratification: Preliminary analyses will check for baseline differences between groups. By using a RCT, we seek to have groups that will be as similar as possible, even in terms of unknown covariates, allowing us to isolate the effect of the intervention.

Should differences remain, we will co-vary variables that are correlated with the outcome and that differ by group. Because we are recruiting from four sites, we will verify that site has no impact on outcomes, either as a main effect or through interactions with treatment. Given block randomization, no differences are expected, particularly no differences in treatment response by site, though we are powered to detect differences between the four sites as low as f=.18 (Cohen's d=.36). In addition to site, responses to the intervention may be further stratified by tumor site (LC vs. HNC) or stage of diagnosis; thus, we will use a block randomization and adjust for imbalance by these variables. We will introduce *fixed effects* to account for stratified randomization in our primary analysis.

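### The added completers-only analysis cannot show whether the result survives non-ignorable dropout; a delta-adjusted analysis of all randomised participants can

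*Combined protocol and SAP*

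**What the plan says.** All references are to the combined protocol and SAP.

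- **Principle.** Section IV.G, Analysis approach: "Using an intent-to-treat (ITT) approach, primary and secondary outcomes will be analyzed with" linear mixed models, for patients and caregivers separately.
- **Main handling of missing data.** Section IV.G, paragraph on missing data and attrition: "Maximum likelihood techniques will include participants with incomplete data without need for imputation". The condition is stated there: "group comparisons will not be biased as long as missing data is ignorable".
- **Sensitivity analyses.** The same paragraph promises analyses of departures from key assumptions and "to help determine effects of missing data". It names no method, no missing-not-at-random model and no range of departures.
- **Completers.** The paragraph then asks whether significance was maintained or "was changed in a limited or large number of sensitivity analyses. If this is the case", and continues that "separate analyses of only those participants who complete the study will be conducted". Completing the study is not defined: it could mean the 6-month visit, all four assessments, or the sessions.
- **Death.** Section IV.C, Randomization and sample size, lists among the reasons for its 20% attrition that participants may "have a member of the couple die". The Step 4 text in the same section lets a caregiver continue after the patient dies. The analysis text in section IV.G does not mention death.

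**The concern.** The likelihood model is sound if dropout depends only on what has been observed. What remains open is whether the conclusion stands if dropout also depends on scores that were never seen. That matters in a lung and head-and-neck cancer population where the plan itself expects 20% (section IV.C) or 24-34% (section IV.G) attrition.

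The completers analysis is the only concrete missing-data step after the main model, and it does not address that question. For its contrast to be valid, completion must in general not depend on the observed post-baseline scores. That is more than the main model needs. If the two results differ, the reader cannot tell whether ignorability failed or the completers were a selected group.

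Dropout that depends on score differently by arm is credible here. In the intervention arm the amount of contact is set by the PROMIS score, from monitoring only up to coping-skills and CBT sessions. The comparison arm receives a resource guide.

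Death adds a second gap. A score after death does not exist, whereas a score after withdrawal exists but is unknown. Completers are survivors by construction, and the likelihood model implicitly extrapolates past death. The plan does not say which quantity it intends.

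**Working it through.** **1. The plan's own figure.** Section IV.C gives 222 randomised per arm and 20% attrition: 222 × 0.80 = 177.6, so 178. With an effect of 0.38 SD and two-sided alpha 0.05/3 = 0.0167, power is Φ(0.38 × √(178/2) − 2.394) = Φ(3.585 − 2.394) = Φ(1.191) = 0.883, close to the stated 90%. This count pools patients and caregivers. The models are fitted separately, so the check below uses 222/2 = 111 per arm.

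**2. Simulation set-up.** From the plan: four assessments, correlation 0.4, dropout of 20% and 34%. Assumed: true effect 0; monotone dropout; log-odds of dropout changing by 1 per SD of the score wherever dropout depends on it. The contrast is change from baseline to 6 months, intervention minus usual care. It was estimated by maximum likelihood on everyone and by simple means in completers, with 500-600 runs per scenario and a Monte Carlo standard error of 0.006-0.008 SD.

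**3. Bias, in SD units.**

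| Dropout depends on | Dropout | Maximum likelihood | Completers |
|---|---|---|---|
| Nothing | 20% | 0.006 | 0.005 |
| Nothing | 34% | −0.007 | −0.003 |
| Last observed score, same in both arms | 20% | 0.009 | 0.012 |
| Last observed score, same in both arms | 34% | −0.001 | 0.000 |
| Last observed score, usual care only | 20% | 0.002 | −0.041 |
| Last observed score, usual care only | 34% | −0.007 | −0.083 |
| Last observed score, opposite directions by arm | 20% | −0.001 | −0.079 |
| Last observed score, opposite directions by arm | 34% | −0.001 | −0.139 |
| Current unseen score, usual care only (non-ignorable) | 20% | 0.089 | 0.046 |
| Current unseen score, usual care only (non-ignorable) | 34% | 0.151 | 0.084 |

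**4. Scale.** Against the 0.38 SD design effect, the opposite-direction biases are 0.079/0.38 = 21% and 0.139/0.38 = 37%. The effect on false positives is Φ(−2.394 + b/s) + Φ(−2.394 − b/s), where b is the bias and s the simulated SD of the completers contrast. For the smallest arm-dependent ignorable case, b/s = 0.041/0.165 = 0.25, giving 2.0%. For the largest, 0.139/0.176 = 0.79, giving 5.5%. The nominal rate is 1.7%. This assumes that the completers analysis is tested at the primary alpha, which the plan does not say.

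**5. What delta does.** Shifting the missing scores in one arm by delta moves that arm's mean by the dropout proportion times delta. With delta set at 0.38 SD purely for illustration, the shift is 0.20 × 0.38 = 0.08 SD at 20% dropout and 0.34 × 0.38 = 0.13 SD at 34%.

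**The case against.** - **The completers analysis is an addition.** A reader might infer that it replaces or overrules the main result when the two disagree. The text does not say so: the analyses are separate, and the likelihood model remains the main analysis. The trigger is also loosely worded. Disagreement among the sensitivity analyses is the natural reading of it, not the only one. This stands, although the plan gives no other step for resolving disagreement.
- **Sensitivity analyses come first.** They cite a paper on intention-to-treat analysis with missing outcomes and a tutorial on sensitivity analyses. Those sources were not available here, so it cannot be claimed that the trial would yield nothing on informative dropout. It can be said that the plan itself names no such method.
- **Completers are not always biased.** A reader might infer bias under any ignorable dropout. The simulations contradict that: with random dropout, or the same mechanism in both arms, the bias was at most 0.012 SD. In the one non-ignorable scenario run, completers were less biased than maximum likelihood (0.05 and 0.08 against 0.09 and 0.15 SD). Both were wrong, however, and nothing in the data would show which was nearer the truth.
- **The dropout models are invented.** No document gives dropout by arm. The sizes illustrate a mechanism and do not forecast this trial. In the smaller cases the effect on false positives is slight.
- **Death is a narrower matter.** The attrition sentence is a recruitment forecast, not an analysis rule, and gives no death rate. Bereaved caregivers may continue, so a patient's death need not remove caregiver scores. A reader might infer that both models are equally affected; the gap lies mainly in the patient model.

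**Conclusion.** The point holds in this limited form. The primary likelihood model is sound under its stated assumption. The weakness is that the one concrete missing-data step after it cannot test that assumption. A completers analysis leaves the intent-to-treat set and generally needs a stronger condition. When ignorable dropout works differently by arm, it gave a false difference of about 0.04 to 0.14 SD on 6-month change at 20% and 34% dropout, or 11% to 37% of the design effect (0.041/0.38 to 0.139/0.38). When the mechanism was the same in both arms the bias was near zero. These figures rest on 111 per arm, correlation 0.4 and assumed dropout models.

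The omission of death is real but secondary, and concerns mainly patients. The plan should be changed before analysis, because as it stands a disagreement between results could not be interpreted. It does not invalidate the main analysis.

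**What to change.** For the primary outcomes, in patients and caregivers separately, pre-specify the following.

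1. **Tipping-point analysis.** Use a delta-adjusted (pattern-mixture) analysis of all randomised participants as the missing-data sensitivity analysis. Impute under the main model's assumption, shift the imputed scores by delta, refit the model, and vary delta separately in each arm until the conclusion at 0.0167 changes. The grid could run at least to 0.38 SD, the plan's own design effect.
2. **Death.** Apply delta only to scores not missing through the participant's own death, and say how visits after death enter. The simplest choice is to leave them missing, as in the main model, so that only delta changes between runs.
3. **Completers.** Define completion and label any completers table as descriptive. Remove the conditional trigger.
4. **Reporting.** Tabulate deaths and other dropout by arm and visit, separately for patients and caregivers. Give means among those alive as descriptive only, because they too condition on survival after randomisation.
5. **Reconcile** the two attrition figures (20% and 24-34%), and the forecast that counts a death in the couple as attrition with the text that lets the caregiver continue.

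The cost is SAP wording and modest programming. The drawback is a range of results that is harder to report than one completers table. Delta adjustment is not the only acceptable non-ignorable method, but it shows directly how much departure would overturn the conclusion.

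### Efficiency, not bias: the group-by-time test leaves baseline unconstrained, which at rho 0.4 costs the equivalent of about 8% to 73% more participants

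*Combined protocol and SAP*

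**What the plan says.** The Analytic Strategy (section IV.G) specifies a linear mixed model, fitted separately in patients and caregivers: "Mixed models will specify group and time and their interaction as fixed effects and subject as a random effect". The outcome is analysed "over 4 times (prior to randomization, 6 weeks, 3 months, 6 months"), so the pre-randomisation score is an outcome and not a covariate. The group-by-time interaction is the hypothesised effect and the stated power target: "The study is powered for testing the hypothesis of no group differences in change over the four time points". It is also a gate: "Planned comparisons of group differences at each time point will be conducted in the event of a significant interaction effect".

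No planned adjustment for the baseline score appears elsewhere. "The patient model of distress will include no a priori covariates", and the caregiver model adds only age and gender in advance. The paragraph on verification of randomisation adds covariates only after a look at the data: "we will co-vary variables that are correlated with the outcome and that differ by group". Its fixed effects for stratified randomisation concern design factors, not the baseline score. On missing data, "Maximum likelihood techniques will include participants with incomplete data without need for imputation". The only within-person dependence named is the subject random effect.

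**The concern.** Randomisation guarantees that the two arms have the same expected score before treatment. A model with free group and group-by-time terms estimates a baseline difference that is known to be zero in expectation, and then measures every follow-up difference against that noisy estimate. The result is unbiased but less precise than it could be.

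The baseline score is collected on everyone, so the precision is available at no cost. It matters more because the interaction test opens the per-visit comparisons: power lost there also blocks them.

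A secondary point concerns the covariance. A single random intercept implies one common correlation between visits that are unequally spaced (about 0, 6, 13 and 26 weeks). If correlation decays with time, the omnibus test no longer holds its nominal level exactly.

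**Working it through.** **Inputs from the protocol.** Rho 0.4, alpha 0.05/3 = 0.0167 and 145 per arm as the analysis target (IV.G, Sample size and power analysis); effect size 0.38, 20% attrition and 178 per arm (IV.C); attrition of 24-34% (IV.G).

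**Assumptions.** Time is categorical, as the per-visit comparisons imply, so the interaction has 3 df. The 0.38 is in SD units (SD = 1). Dropout is monotone and evenly spread. The effect shapes below are illustrative.

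**The plan's own figure.** Section IV.C gives 90% power for 0.38 with 178 per arm. A two-sample comparison at alpha 0.0167 gives 88.3% (88.0% by noncentral t), close to the stated figure. The 90% therefore fits a simple two-group comparison of pooled participants, not the interaction test.

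**Formulas, complete data.** Let d be the three follow-up effects and n the number per arm.

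- Planned test: λp = (n/2)·[Σd² − (Σd)²/4]/(1 − ρ), with 3 and 3(2n − 2) df.
- Common baseline mean: λa = (n/2)·d′S⁻¹d, with S = 0.6I + 0.24J at ρ = 0.4, that is (n/2)·[Σd² − 0.1818(Σd)²]/0.6, with 3 and 2n − 5 df.
- Difference: λa − λp = (n/2)·0.1136·(Σd)², never negative. Both tests have 3 df, so the sample-size ratio is λa/λp.

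**Example.** Constant effect, d = 0.38 at all three visits, n = 145: Σd² = 0.4332 and (Σd)² = 1.2996.

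- λp = 72.5 × (0.4332 − 0.3249)/0.6 = 13.09
- λa = 72.5 × (0.4332 − 0.2363)/0.6 = 23.79
- Ratio = 1.82

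**Partial data.** The same comparison uses generalised least squares information. The numbers per arm at the four times are 181/169/157/145 for the 145 target, and 111/104/96/89 for about half of the pooled 222 and 178, because patients and caregivers are analysed separately.

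| Effect shape | Ratio, complete | Ratio, 20% dropout | Ratio, 34% dropout | Power at 145, partial data | Power at 89, partial data |
|---|---|---|---|---|---|
| Constant | 1.82 | 1.73 | 1.66 | 84% → 98% | 57% → 85% |
| Linear in visit number | 1.49 | 1.44 | 1.41 | 63% → 82% | 37% → 55% |
| Linear in weeks | 1.37 | 1.33 | 1.31 | 62% → 77% | 36% → 49% |
| 6 months only | 1.09 | 1.08 | 1.06 | 77% → 80% | 49% → 52% |
| Fading (0.38/0.19/0) | 1.22 | 1.23 | 1.24 | 78% → 87% | 51% → 61% |

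Each power cell shows the planned test, then the same test with a common baseline mean. With 145 complete cases the five pairs are 76% → 97%, 59% → 81%, 59% → 76%, 76% → 80% and 71% → 81%.

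**Sensitivity to rho.** At rho 0.6 the ratios fall to 1.05-1.43 (complete) and 1.04-1.39 (20% dropout), and the gains at 145 complete fall to 1 to 9 points.

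**Sensitivity to equal correlation.** With both tests given the correct covariance and complete data, the range is 1.05-1.69 for correlations of 0.60/0.36/0.22 at one, two and three visits apart, and 1.05-1.89 for exponential decay in weeks with mean correlation 0.4.

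**Covariance and Type I error.** These come from 20,000 simulated complete-data trials per pattern (nominal 1.67%, simulation SE 0.09 points). The planned omnibus test rejects in 1.6-1.7% under equal correlation and 2.4-2.7% under the two decay patterns. Plain per-visit follow-up differences reject in 1.5-1.9% ungated and 0.2-0.5% after the gate. An unstructured test with baseline as covariate stays at 1.6-1.7%.

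**The case against.** The strongest reply is that nothing here is an error. The plan names one valid test, powers it and hypothesises it consistently; a more efficient estimator is only an improvement. That is right, and the point claims no more.

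The size is also open to challenge, and much of that challenge stands:

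- The top of the range needs the full effect at 6 weeks, held unchanged to 6 months. The only evidence on shape in the document, a small caregiver pilot (section III) with a greater reduction at 6 months than at 3, suggests a building effect, where the cost is 33-44%.
- The figures depend on rho and on dropout timing, which the plan does not give.
- The 3 df and the reading of 0.38 as an SD difference at a visit are inferences.
- "Our target sample size for analyses is 290 patients and 290 caregivers (145 per arm") cannot be reached from 222 randomised patients, which is 222/2 = 111 per arm. At attainable numbers the building-effect shapes rise only from 36-37% to 49-55%. The change recovers efficiency; it does not by itself restore adequate power.
- The covariance point rests on assumed decay patterns. Its simulations used complete data and the covariate form of the adjusted test, not the common-baseline form.

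The conditional covariate rule does not answer the point. It acts only on chance imbalance and does not recover the lost precision.

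**Conclusion.** The concern holds as a recommendation on efficiency. Under rho 0.4, equal correlation, same-direction effects and 20% evenly spread monotone dropout, the planned test costs the equivalent of 8% to 73% more participants (9% to 82% with complete data; 6% to 66% at 34% dropout). At 145 per arm with partial data the gain from a common baseline mean is 3 to 19 percentage points; at about 89 per arm in each population it is 3 to 28. The gain is small if the effect appears at one visit only or if rho is high, and nil if follow-up effects cancel. The covariance point is a lesser safeguard: omnibus error rises modestly under assumed decay, and the plain per-visit differences are not inflated.

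**What to change.** In PROC MIXED, keep all four times as outcomes but constrain the arms to a common baseline mean. Replace the free group and group-by-time terms with three treatment terms, one per follow-up visit and each zero at baseline, and test them jointly on 3 df. With a common baseline mean, no group difference at any follow-up is the same hypothesis as no group difference in change, so the alpha and the gate can stay. Participants with only a baseline score remain in the model.

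The alternative is to use the baseline score as a covariate with three follow-up outcomes. The test must then be the joint group plus group-by-time effect (3 df), because the interaction alone would miss a constant effect. With complete data at rho 0.4, the variance of each per-visit comparison falls from 1.00 to 0.84.

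As a secondary safeguard, state an unstructured covariance over visits (REPEATED, TYPE=UN) with Kenward-Roger degrees of freedom.

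The cost is SAP wording, a few lines of SAS and a few more covariance parameters. The adjusted power figures above already allow for those parameters through fewer denominator df.
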